Appendix 3 International Neuroblastoma Response Criteria (cont.)

Table 1 Overall Response at Any Timepoint

CT/MRI Lesions	MIBG Lesions	Bone Marrow	Catechols	Overall Response
PD	Any	Any	Any	PD
Any	PD	Any	Any	PD
Any	Any	PD	Any	PD
CR	CR	CR	Normal	CR
VGPR	CR in bone lesions ; May have SD/CR in soft tissue sites corresponding to lesions on CT/MRI	CR	Normal	VGPR
PR	PR/CR in bone lesions; May have SD/CR in soft tissue sites corresponding to lesions on CT/MRI	CR	Any	PR
SD	SD	SD	Any	SD
SD/PR/VGPR/CR	SD	SD/CR	Any	SD
SD/PR/VGPR/CR	SD/PR/CR	SD	Any	SD

CR= complete response; CT=computed tomography; MRI=magnetic resonance imaging; PD=progressive disease; PR=partial response; SD=stable disease; VGPR=very good partial response.

Appendix 4

Revised Response Criteria for Malignant Lymphoma

SELECTION OF TARGET LESIONS

Up to six of the largest dominant nodes or tumor masses selected according to all of the following:

- Clearly measurable in at least two perpendicular dimensions
 - All nodal lesions must measure:
 - > 1.5 cm in greatest transverse diameter (GTD) regardless of short axis measurement, or
 - > 1.0 cm in short axis regardless of the GTD measurement
 - All extranodal lesions must measure ≥ 10 mm in the GTD and twice the reconstruction interval of the scan.
 - Extranodal lesions within the liver or spleen must be at least 1.0 cm in two perpendicular dimensions
- If possible, they should be from disparate regions of the body
- Should include mediastinal and retroperitoneal areas of disease whenever these sites are involved

Measurable extranodal disease should be assessed in a manner similar to that used for nodal disease.

SELECTION OF NON-TARGET LESIONS

Non-target lesions will be qualitatively assessed at each subsequent timepoint. All of the sites of disease present at baseline and not classified as target lesions will be classified as non-target lesions, including any measurable lesions that were not chosen as target lesions. Examples of non-target lesions include:

- All bone lesions, irrespective of the modality used to assess them
- Lymphangitis of the skin or lung
- Cystic lesions
- Splenomegaly and hepatomegaly
- Irradiated lesions
- Measurable lesions beyond the maximum number of six
- Groups of lesions that are small and numerous
- Pleural/pericardial effusions and/or ascites

Appendix 4

Revised Response Criteria for Malignant Lymphoma (cont.)

For this study, a significant increase in existing pleural effusions, ascites, or other fluid collections will be considered sufficient evidence of progression and will not require cytological proof of malignancy. Effusions, ascites, or other fluid collections will be followed as non-target lesions.

- **Existing effusions/ascites:** Effusions, ascites, or other fluid collections will be followed as non-target lesions. At each timepoint, radiologists will check for the presence or absence of effusions/ascites. If there is a significant volume increase in the absence of a benign etiology, progression can be assessed.
- **New effusions/ascites:** Significant new effusions, ascites, or other fluid collections, which are radiographically suggestive of malignancy, should be recorded as new lesions.

REPORTING CONVENTIONS

UNABLE TO EVALUATE (UE) LESION CATEGORY

This category is reserved for target and non-target lesions that are deemed unevaluable because 1) subsequent (post-baseline) examinations had not been performed, 2) lesions could not be evaluated because of poor radiographic technique or poorly defined margins, or 3) lesions identified at baseline were not at a subsequent timepoint.

Examples of UE lesions are a lung lesion in the hilum obstructing the bronchus and causing atelectasis of the lobe or a hypodense liver lesion that becomes surrounded by fatty infiltration. In both examples the boundaries of the lesion can be difficult to distinguish. Every effort should be made to assign measurements to lesions that develop less distinct margins because they become much smaller. Another example is the instance when lesions identified at baseline were not imaged at a subsequent timepoint. Lesions that cannot be measured or evaluated will be classified for that timepoint as UE.

If a target lesion is classified as UE post-baseline, the sum of the product of the diameters (SPD)/area (whichever applies) of the target lesions cannot accurately be determined for that timepoint, a response of complete response (CR), partial remission (PR), or stable disease (SD) cannot be assigned for that timepoint, and the response assessment will be UE unless unequivocal progression is determined on the basis of non-target or new lesions or the evaluable target lesions.

Progressive disease (PD) can be determined without evaluation of all sites of disease based on the greatest transverse diameter (GTD), area or SPD for target lesions, evaluation of unequivocal progression in non-target lesions, or observation of a new lesion within the available radiographic or clinical assessments.

Appendix 4

Revised Response Criteria for Malignant Lymphoma (cont.)

TOO SMALL TO MEASURE (TSTM) LESION CATEGORY

Any target lesion findings identified on baseline images, which at a subsequent timepoint decreases in size to <5 mm in any dimension, should be categorized as TSTM. The lesion, node, or mass should be assigned measurements of 5 × 5 mm (for the GTD and the short axis) on the source document for the purposes of calculating the area. If that lesion increases in size to ≥5 mm in any dimension afterwards, its true size (GTD and short axis) should be recorded. The purpose of the assigned value for the measurement is the acknowledgment that small findings are not accurately measured.

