6.1 DETERMINATION OF SAMPLE SIZE

No formal hypothesis testing is planned in this study.

A minimum of 40 patients will be enrolled in this study across all tumor types. In addition, at least two tumor type cohorts must enroll a minimum of 10 patients. To make a preliminary assessment of the efficacy of the study drug, two response assessments are planned: an initial response assessment and an additional response assessment. Taking into account historical control ORRs for each pediatric tumor type, the minimum number of patients in the initial response assessment and the minimum number of responders needed for cohort expansion and advancement to the additional response assessment were calculated and are presented by tumor type in [Table 3](#). Given the bony nature of osteosarcoma, responses in osteosarcomas do not always result in tumor shrinkage as the extracellular matrix produced by the tumor cells does not always disappear even when the cells die ([Benjamin RS 2015](#)). Thus, for osteosarcoma, CBR instead of objective response was considered in the response assessment. Patients with osteosarcoma are considered to have CBR if they have objective response or stable disease for at least 6 months, as determined by RECIST v1.1.

An initial response assessment will consider any available preclinical data in addition to any early efficacy or safety signals seen in the tumor type cohorts (enrollment may be closed while the response assessments are being conducted). The selection of expansion cohorts for additional response assessment, as well as the number of patients needed for the additional response assessment, will also take into account practical considerations (e.g., enrollment feasibility), biomarker analysis, safety profiles, and any other relevant information. The maximum number of patients per tumor type cohort will be 40. Similar consideration will be given to other rare pediatric tumor types that are enrolled in the study and not included in [Table 3](#).

Table 3 Sample Size and Responder Requirements for Initial Response Assessment

Disease (Relapsed/Refractory)	Historical Control Objective Response Rate (%)	Initial Response Assessment	
		Minimum No. of Patients Enrolled	Minimum No. of Responders Needed for Tumor Type Cohort Expansion
Hepatoblastoma	10%	10	2
Hodgkin's disease	60 ^a	14	10
Wilms tumor	10	10	2
Neuroblastoma	18	10	3
Non-Hodgkin's lymphoma	40 ^a	12	6
High-grade osteosarcoma	20 ^b	10	3
Rhabdomyosarcoma	10	10	2

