Patient may be declared to have PD in bone marrow after only one diagnostic bone marrow at the discretion of the treating physician
Patients who enter study with bone marrow tumor by morphology will be considered to have PD if there is a minimum of 25% tumor in the marrow by morphology and a doubling in the amount of tumor in the marrow compared with the level present at study entry. For example, a patient entering with 5% tumor in marrow by morphology must increase to >25% tumor to have PD; a patient entering with 30% tumor must increase to >60% tumor.
- SD: Persistence of an amount of tumor in the bone marrow by morphology that does not meet criteria for either CR or PD
Patients who clear morphologic tumor but have immunocytologic tumor will be called SD.

RESPONSE CRITERIA FOR MIBG-POSITIVE LESIONS

All patients with known MIBG-avid lesions will be evaluable for MIBG response following the first course of therapy. The following criteria will be used to report MIBG response:

- CR: Complete resolution of all MIBG-positive lesions
- PR: Resolution of at least one MIBG-positive lesion, with persistence of other MIBG positive lesions
- SD: No change in MIBG scan in number of positive lesions (includes patients who have same number of positive lesions but decreased intensity)
- PD: Development of new MIBG-positive lesions

Appendix 3

International Neuroblastoma Response Criteria (cont.)

DEFINITION OF OVERALL RESPONSE FOR EACH PATIENT WITH NEUROBLASTOMA

The International Neuroblastoma Response Criteria were developed to define responses in patients being treated with frontline therapy from diagnosis.¹ These criteria were utilized as a basis for the following response criteria, which integrate response at all sites defined as measurable in this study, including CT/MRI lesions that meet RECIST criteria, MIBG-positive lesions, and bone marrow disease. These criteria will be used to define the overall response for each patient.

- CR: Disappearance of all target lesions; no evidence of tumor at any site (chest, abdomen, liver, bone, bone marrow, nodes, etc.); homovanillic acid (HVA) and vanillylmandelic acid (VMA) normal

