- VGPR: Greater than 90% decrease of the disease measurement for CT/MRI target lesions, taking as reference the disease measurement done to confirm measurable disease in target lesions at study entry; all preexisting bone lesions with CR by MIBG; MIBG scan can be \pm or CR in soft tissue lesions corresponding to lesions on CT/MRI; CR in bone marrow; no new sites of tumor; HVA/VMA normal
- PR: At least a 30% decrease in the disease measurement for CT/MRI target lesions, taking as reference the disease measurement done to confirm measurable disease in target lesions at study entry; bone marrow with CR; MIBG with either PR or CR in bone lesions; MIBG may be SD or CR in soft tissue lesions corresponding to lesions on CT/MRI; HVA/VMA may still be elevated.
- PD: Any one of the following:
 - At least a 20% increase in the disease measurement for CT/MRI target lesions, taking as reference the smallest disease measurement recorded since the start of treatment
 - Appearance of one or more new lesions or new sites of tumor
 - PD as defined above for either bone marrow or MIBG lesions
- SD: Stable disease by either CT/MRI lesion, bone marrow, or MIBG criteria; no new lesions; no new sites of disease

The overall response as assessed at any particular timepoint based on the various disease sites is summarized in the table below.

¹ Brodeur GM, Pritchard J, Berthold F, et al. Revisions of the international criteria for neuroblastoma diagnosis, staging, and response to treatment. *J Clin Oncol* 1993;11:1466–77.

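### Neuroblastoma overall response: Appendix 3 Table 1 leaves some deep CT responders without a row and, for patients with soft-tissue MIBG lesions only, depends on an unstated convention

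*Combined protocol and SAP*

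**What the plan says.** Appendix 3 of the protocol first grades each compartment (CT/MRI, MIBG, marrow) and then defines overall response in text. It says the text criteria define each patient's overall response and that Table 1 summarises them.

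- **Text PR, CT part:** "PR: At least a 30% decrease in the disease measurement for CT/MRI target lesions". There is no upper limit.
- **Text PR, other compartments:** "bone marrow with CR; MIBG with either PR or CR in bone lesions; MIBG may be SD or CR in soft tissue lesions", and "HVA/VMA may still be elevated".
- **Text CR** requires "homovanillic acid (HVA) and vanillylmandelic acid (VMA) normal".
- **MIBG SD** is "No change in MIBG scan in number of positive lesions (includes patients who have same number of positive lesions but decreased intensity").
- **Text SD** is stable disease by any one of CT/MRI, marrow or MIBG, with no new lesions or sites.
- **Table 1, PR row:** CT PR, marrow CR, any catecholamines, and MIBG PR or CR in bone lesions, with the addition "May have SD/CR in soft tissue sites corresponding to lesions on CT/MRI".

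Section 6.6.1 counts a confirmed complete or partial response, determined by the investigator, toward ORR. Table 3 in Section 6.1 sets 3 responders in 10 patients as the neuroblastoma minimum for cohort expansion. The same section states: "No formal hypothesis testing is planned in this study".

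**The concern.** A summary table should give every patient one result, and the same result as the definitions it summarises. Table 1 fails on both counts. A patient whose CT lesions have disappeared can have no row, while an otherwise identical patient with a 30% reduction is scored PR. A patient whose only MIBG-avid disease is in soft tissue can match two rows with different results, depending on a convention that the appendix does not state.

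Response is assigned by investigators at about 50 sites (Section 3.1.1). One may work from the text and another from the table. The affected classifications include responder versus non-responder, so they bear on a primary efficacy endpoint and on the cohort's expansion count. The requirement to confirm a response at least 4 weeks later does not help, because each timepoint must first be classified.

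**Working it through.** **Table 1, rows numbered from the top.** Rows 1–3 are the PD rows. The others are:

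| Row | CT/MRI | MIBG | Marrow | Catechols | Overall |
|---|---|---|---|---|---|
| 4 | CR | CR | CR | Normal | CR |
| 5 | VGPR | CR in bone; soft tissue SD/CR | CR | Normal | VGPR |
| 6 | PR | PR/CR in bone; soft tissue SD/CR | CR | Any | PR |
| 7 | SD | SD | SD | Any | SD |
| 8 | SD/PR/VGPR/CR | SD | SD/CR | Any | SD |
| 9 | SD/PR/VGPR/CR | SD/PR/CR | SD | Any | SD |

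There is no stated plan figure to reproduce; this is a check of logic.

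**Step 1: gaps, with MIBG lesions in bone only.** CT (CR, VGPR, PR, SD) × MIBG (CR, PR, SD) × marrow (CR, SD) × catechols (normal, elevated) = 4 × 3 × 2 × 2 = 48 combinations. Those with no row all have marrow CR:

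| CT | MIBG and catechols | Count | Text result |
|---|---|---|---|
| CR | CR elevated; PR normal; PR elevated | 3 | PR |
| VGPR | CR elevated; PR normal; PR elevated | 3 | PR |
| SD | CR or PR, either catechol result | 4 | SD |

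Total 3 + 3 + 4 = 10. With CT PR in place of CT CR or VGPR, the first six profiles all fall in row 6 and are PR.

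**Step 2: separate bone and soft-tissue MIBG.** Each site is none, CR, PR or SD, excluding none in both: 4 × 4 − 1 = 15 MIBG profiles. The grid is 4 × 15 × 2 × 2 = 240. The whole-scan MIBG grade is taken as CR if all sites are CR, SD if all are SD, and PR otherwise.

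| Bone condition when no bone lesions exist | No row | Of these, meeting text PR | Rows giving different results |
|---|---|---|---|
| Counts as met | 75 | 21 | 3 |
| Counts as not met | 78 | 19 | 0 |

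**Step 3: soft-tissue-only patients with MIBG SD and marrow CR.**

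- *Condition met.* CT PR with normal or elevated catechols matches row 6 (PR) and row 8 (SD). CT VGPR with normal catechols matches row 5 (VGPR) and row 8 (SD). These are the three conflicts. CT CR matches only row 8 (SD), although the text supports VGPR or PR.
- *Condition not met.* The conflict disappears, but a soft-tissue-only patient can never reach row 6. With CT PR and marrow CR, MIBG CR has no row and MIBG SD falls in row 8.

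The table gives no order of precedence. The text SD definition does not break the tie, because such a patient is stable by MIBG while also meeting the wording of text PR. Patients with a resolved bone lesion do not overlap, because their whole-scan MIBG grade is PR or CR.

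**Step 4: sensitivity of the expansion minimum (illustration only).** Losing one responder changes the outcome only if the count would otherwise be exactly 3. For a binomial with n = 10, P(exactly 3) = P(≥3) − P(≥4):

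- At the historical 18%: 0.263 − 0.088 = 0.175.
- At an assumed 30%: 0.617 − 0.350 = 0.267.

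This shows how close to the minimum a cohort may sit. It does not estimate how often a misclassification would occur.

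**The case against.** The strongest reply is that the text already settles the no-row cases. Appendix 3 says its text criteria define overall response and calls the table a summary. Under the text, the six CT CR or VGPR cases are PR and the four CT SD cases are SD; the latter cannot affect ORR. That stands: this is a faulty summary table, not an undefined endpoint. But no sentence says that the text prevails where the two differ, and on soft-tissue-only disease the text has the same tension between its PR and SD definitions.

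It also stands that the double match depends on how absent bone lesions are read. Row 6 largely repeats the text PR wording, so the clash is between rows 6 and 8 rather than between row 6 and the text.

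A reader might infer that Table 1 will be programmed and that patients without a row will be lost from ORR. The documents do not support this. Response is determined by the investigator, no section says ORR is derived from the table by program, and the only stated non-responder rule in Section 6.6.1 concerns patients with no post-baseline assessment.

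The expansion minimum is also not an automatic stop. Under Section 3.1.2, enrollment may be stopped if it is missed, and exceptions are allowed for a strong signal in a slow-enrolling, rare cohort.

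**Conclusion.** The point holds in two parts. The first is unconditional: Table 1 omits combinations that the text classifies, 10 of 48 on the simple grid, six of them PR under the text. The second is conditional: with no bone MIBG lesions, the table either gives conflicting results or shuts soft-tissue-only patients out of the PR row. Both readings need repair.

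The effect is possible inconsistency between investigators in classifying neuroblastoma patients, which bears on ORR and may bear on the 3-of-10 minimum. It is tempting to turn this into a loss in the probability of reaching 3 of 10. That would require the share of responders with these profiles and the assumption that each is scored a non-responder. The documents give neither, so the size cannot be stated. The combination counts are counts of table cells, not of patients, and the 240-cell counts rest on the whole-scan MIBG convention in Step 2. The correction is worth making because it is cheap and concerns a primary endpoint.

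**What to change.** Reconcile Table 1 with the text of Appendix 3 and state that the text governs. Specifically:

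- **VGPR row:** also accept CT CR when overall CR is not met.
- **PR row:** accept CT PR, VGPR or CR when overall CR or VGPR is not met.
- **Absent bone lesions:** state that the bone-MIBG condition is met when there are no bone lesions at baseline.
- **Row 8:** limit it to (a) CT SD with any MIBG SD, or (b) CT PR, VGPR or CR with MIBG SD in bone lesions that are present. Restricting the whole row to bone lesions would not work, because a soft-tissue-only patient with CT SD, MIBG SD and marrow CR would then have no row.
- **New row:** CT SD, MIBG PR or CR, marrow CR, giving SD.
- **Soft-tissue MIBG PR:** state how it is handled. The text names only SD or CR, so this is a decision about the criteria and not just a table correction.

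Applied to the 240-cell grid, these edits leave no conflicting rows. If soft-tissue MIBG PR is accepted in the VGPR and PR rows, no cell is without a row. If it is left unaddressed, 18 cells remain: CT CR, VGPR or PR (3) × bone none, CR or PR (3) × two catechol results (2), with soft-tissue PR and marrow CR.

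The cost is one appendix table, a few sentences and a note to sites. No new data are needed. Any neuroblastoma timepoints already assessed with these profiles should be rechecked.

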Appendix 4 Revised Response Criteria for Malignant Lymphoma (cont.)

Timepoint Response

Target Lesions	Non-Target Lesions	New Lesions ^a	Timepoint Response
CR	CR	No	CR
CR	SD	No	PR
CR	UE	No	UE
PR	UE	No	UE
PR	CR	No	PR
PR	SD	No	PR
SD	UE	No	UE
SD	CR	No	SD
SD	SD	No	SD
PD	Any	Yes/No	PD
Any	PD	Yes/No	PD
Any	Any	Yes	PD
UE	Non-PD	No	UE
UE	UE	No	UE
CR	NA ^c	No	CR
PR	NA ^c	No	PR
SD	NA ^c	No	SD
NA ^b	SD	No	SD
NA ^b	CR	No	CR
NA ^b	UE	No	UE
NA ^b	NA ^c	No	UE

CR=complete response; NA=not applicable; PD=progressive disease; PR=partial response; SD=stable disease; UE=unable to evaluate.

Note: Modified from Cheson BD, Pfistner B, Juweid ME, et al. Revised response criteria for malignant lymphoma. J Clin Oncol 2007;25:579–86.

^a Identification of new lesions at a post-baseline time point will result in a response assessment of PD. If an identified new lesion subsequently becomes UE, the timepoint response will be recorded as PD unless the new lesion has proven to have resolved.

^b No target lesions identified at baseline.

^c No non-target lesions identified at baseline.

Appendix 4

Revised Response Criteria for Malignant Lymphoma (cont.)

Response should be determined on the basis of radiographic and clinical evidence of disease. For the end-of-treatment response assessment, an FDG-PET will be performed 6–8 weeks after the last study treatment. Assessment of PET should follow the criteria described by Juweid et al. 2007, which is presented in the table Response Definitions for Clinical Trials.

COMPLETE RESPONSE

- Complete disappearance of all detectable clinical evidence of disease and disease-related symptoms if present before therapy
- Typically ¹⁸F-fluorodeoxyglucose (FDG)–avid lymphoma: in patients with no pre-treatment positron emission tomography (PET) scan or when the PET scan was positive before therapy, a post-treatment residual mass of any size is permitted as long as it is PET negative.
- Variably FDG-avid lymphomas/FDG avidity unknown: in patients without a pre-treatment PET scan, or if a pre-treatment PET scan was negative, all lymph nodes and nodal masses must have regressed on CT to normal size (≤ 1.5 cm in their greatest transverse diameter for nodes > 1.5 cm before therapy). Previously involved nodes that were 1.1 to 1.5 cm in their long axis and > 1.0 cm in their short axis before treatment must have decreased to ≤ 1.0 cm in their short axis after treatment.
- The spleen and/or liver, if considered enlarged before therapy on the basis of a physical examination or CT scan, should not be palpable on physical examination and should be considered normal size by imaging studies, and nodules related to lymphoma should disappear. However, determination of splenic involvement is not always reliable because a spleen considered normal in size may still contain lymphoma, whereas an enlarged spleen may reflect variations in anatomy, blood volume, the use of hematopoietic growth factors, or causes other than lymphoma.
- If the bone marrow was involved by lymphoma before treatment, the infiltrate must have cleared on repeat bone marrow biopsy. The biopsy sample on which this determination is made must be adequate (with a goal of > 20 mm unilateral core). If the sample is indeterminate by morphology, it should be negative by immunohistochemistry. A sample that is negative by immunohistochemistry but that demonstrates a small population of clonal lymphocytes by flow cytometry will be considered a CR until data become available demonstrating a clear difference in patient outcome.

Appendix 4

Revised Response Criteria for Malignant Lymphoma (cont.)

PARTIAL RESPONSE

- At least a 50% decrease in SPD of up to six of the largest dominant nodes or nodal masses. These nodes or masses should be selected according to all of the following: they should be clearly measurable in at least two perpendicular dimensions; if possible they should be from disparate regions of the body; and they should include mediastinal and retroperitoneal areas of disease whenever these sites are involved.
- No increase should be observed in the size of other nodes, liver, or spleen.
- Splenic and hepatic nodules must regress by $\geq 50\%$ in their SPD or, for single nodules, in the GTD.
- With the exception of splenic and hepatic nodules, involvement of other organs is usually assessable and no measurable disease should be present.
- Bone marrow assessment is irrelevant for determination of a PR if the sample was positive before treatment. However, if positive, the cell type should be specified (e.g., large-cell lymphoma or small neoplastic B cells). Patients who achieve a CR by the above criteria but who have persistent morphologic bone marrow involvement will be considered partial responders. If the bone marrow was involved before therapy and a clinical CR is achieved, but with no bone marrow assessment after treatment, patients should be considered partial responders.
- No new sites of disease should be observed.
- Typically FDG-avid lymphoma: for patients with no pre-treatment PET scan or if the PET scan was positive before therapy, the post-treatment PET should be positive in at least one previously involved site.
- Variably FDG-avid lymphomas/FDG-avidity unknown: for patients without a pre-treatment PET scan, or if a pre-treatment PET scan was negative, CT criteria should be used.

In patients with follicular lymphoma or mantle-cell lymphoma, a PET scan is only indicated with one or at most two residual masses that have regressed by more than 50% on CT; those with more than two residual lesions are unlikely to be PET negative and should be considered partial responders.

Appendix 4

Revised Response Criteria for Malignant Lymphoma (cont.)

STABLE DISEASE

- A patient is considered to have SD when he or she fails to attain the criteria needed for a CR or PR but does not fulfill those for progressive disease (PD) (see Relapsed Disease [after Complete Response] or Progressive Disease [after Partial Response or Stable Disease]).
- Typically FDG-avid lymphomas: the PET should be positive at prior sites of disease with no new areas of involvement on the post-treatment CT or PET.
- Variably FDG-avid lymphomas/FDG-avidity unknown: for patients without a pre-treatment PET scan or if the pre-treatment PET was negative, there must be no change in the size of the previous lesions on the post-treatment CT scan.

RELAPSED DISEASE (AFTER COMPLETE RESPONSE) OR PROGRESSIVE DISEASE (AFTER PARTIAL RESPONSE OR STABLE DISEASE)

Lymph nodes should be considered abnormal if the long axis is more than 1.5 cm, regardless of the short axis. If a lymph node has a long axis of 1.1 to 1.5 cm, it should only be considered abnormal if its short axis is more than 1.0. Lymph nodes $\leq 1.0 \times \leq 1.0$ cm will not be considered as abnormal for relapse or progressive disease.

- Appearance of any new lesion > 1.5 cm in any axis during or at the end of therapy, even if other lesions are decreasing in size. Increased FDG uptake in a previously unaffected site should only be considered relapsed or progressive disease after confirmation with other modalities. In patients with no prior history of pulmonary lymphoma, new lung nodules identified by CT are mostly benign. Thus, a therapeutic decision should not be made solely on the basis of the PET without histologic confirmation.
- At least a 50% increase from nadir in the SPD of any previously involved nodes, or in a single involved node, or the size of other lesions (e.g., splenic or hepatic nodules). To be considered PD, a lymph node with a diameter of the short axis < 1.0 cm must increase by $\geq 50\%$ and to a size of 1.5×1.5 cm or > 1.5 cm in the long axis.
- At least a 50% increase in the longest diameter of any single previously identified node > 1 cm in its short axis.
- Lesions should be PET positive if observed in a typical FDG-avid lymphoma or the lesion was PET positive before therapy unless the lesion is too small to be detected with current PET systems (< 1.5 cm in its long axis by CT).

Measurable extranodal disease should be assessed in a manner similar to that for nodal disease. For these recommendations, the spleen is considered nodal disease. Disease that is only assessable (e.g., pleural effusions, bone lesions) will be recorded as present

Appendix 4

Revised Response Criteria for Malignant Lymphoma (cont.)

or absent only, unless, while an abnormality is still noted by imaging studies or physical examination, it is found to be histologically negative.

In clinical trials where PET is unavailable to the vast majority of participants, or where PET is not deemed necessary or appropriate for use (e.g., a study involving patients with mucosa-associated lymphoid tissue lymphoma), response should be assessed as above but only using CT scans. However, residual masses should not be assigned unconfirmed complete response status but should be considered partial responses.

